5.10.4.7 Safety Analyses

The safety analysis will be based on the pre-defined population (as above). Summary tables will be presented for incidence rates (number of patients with at least one incidence) of adverse events and SAEs coded according to the section 5.11.3.1 of the protocol.

5.10.5 Economic evaluation

An economic evaluation will be conducted alongside the randomised controlled trial. The form of this study will be a cost-utility analysis and the perspective will be societal, i.e. will include NHS and social services as well as costs incurred by participants. The comparisons evaluated in the economic evaluation will be the same groups as in the main trial, i.e., control (TAU), TAU plus hospital based exercise; and TAU plus home based exercise. The outcome measure used in the economic evaluation will be the quality adjusted life year (QALY). The QALY is calculated by multiplying duration of life by a measure of health related quality of life. HR-QoL will be estimated using two different instruments; the EQ-5D-5L (where 5L denotes five levels) and the SF-6D. The SF-6D will be obtained from SF-36, which is also being collected in this study. These instruments will be used to generate preference weightings for the calculations of QALYs using UK specific preference weights. Both the EQ-5D-5L and SF36 will be collected at 4 time points, baseline, 30 days post-operation and 6 and 12-months post-randomisation.

We will record all resources required to provide the two exercise interventions. Costs of the intervention will fall under a number of categories. Firstly, there will be any training required to ensure the intervention is provided in a consistent way. Staff time required to provide this training will be recorded, including appropriate preparation time as well as actual time of provision. Additionally, numbers of staff attending these sessions should be recorded by means of registers. Provision of the intervention will require staff time to supervise the group sessions. Time is also likely to be required in preparation for sessions and for administrative tasks. A sample of staff will be asked to complete a diary for a representative period of time to estimate time spent in providing contacts with participants and time spent on other tasks required. Each centre should record what facilities and equipment are required to provide the intervention and record any study expenditure on equipment. A similar process would be carried out for the home based exercise. A member of the Trial Intervention Team will record attendance at an initial 45 minute exercise counselling session. For the hospital based exercise group participant attendance at the group sessions should be recorded. These data will be entered directly onto the study eCRF. For the post-operative period attendance at the monthly booster sessions will be recorded on study eCRF. Details of exercise, both before and after surgery should be recorded on patient exercise diaries. These data on the resource required to provide the exercise interventions and the utilisation of exercise sessions in both groups will enable an estimate of the cost per person of the two exercise interventions.

For the home-based group in the pre-operative period we will record time required to provide telephone support by a member of the Trial Intervention Team as well as attendance at the 45 minute exercise counselling session. Post-operatively the home based group will receive a 15 minute motivational telephone call monthly from a member of the Trial Intervention Team, again this will be recorded on the eCRF. Finally, both groups will receive information on local exercise facilities. In order to quantify any effects that the exercise interventions may have on health care received, we will estimate costs of providing healthcare in all participants. Secondary care costs are likely to be an important component of total costs so relevant resource use will be collected, including: operating time, time in ICU/ITU, length of stay, complications, re-operations, and need for re-admissions. These data will be recorded by study researchers from patient notes or hospital data at each site and recorded onto the eCRF. This will cover the duration of the 12 months follow up.

Other health care related resource use data will be collected via a patient-completed questionnaire, completed at baseline, and at 6 and 12 months post-randomisation. These data will be collected by means of a modified CSRI. Care will be taken to ensure that the forms are as simple as possible. It is anticipated that all care related to the secondary care received in the study hospital to which the patient is recruited will be collected directly from patient notes and hospital records. Therefore the modified CSRI will cover primary care services; prescribed medicines; social care; and own borne costs. Because of the requirement for attending hospital to receive exercise in the hospital exercise group these patients will be required to visit the hospital more often and hence may incur higher travel costs. Therefore it is important to quantify the costs borne by participants in attending hospital. Participants in the hospital exercise group are reimbursed travel expenses and these will be recorded in the eCRF to reflect extra costs incurred by this group. Relevant costs borne by participants would also include any out of pocket expenses. We will also collect data on time off work. Participants will self-complete these questionnaires. If a questionnaire is not returned then participants will be sent one reminder.

For all resource use data quantities will be multiplied by unit costs from standard NHS and other data sources (e.g. PSSRU and NHS Reference Costs) to estimate the cost per patient in each arm over one year. In the case of the costs of the intervention no representative cost will be available and a bespoke cost of the intervention will be calculated using resource use data collected as part of the study.

5.10.5.1 Health Economic Analysis Plan

A full health economics Analysis Plan (HEAP) will be developed between the trial health economist, Chief Investigators and trial statistician before any analysis is undertaken. The HEAP will be shared with the trial's governance committees.

5.10.5.2 Within-trial analysis

The health economic analysis will be carried out on an 'intention to treat' basis. For each of the 3 study groups we will estimate costs for the 12 months of the study follow-up. Total costs will include costs of providing the interventions, cost of secondary care, and costs incurred in primary care. We will also estimate costs borne by study participants as well as productivity costs incurred through time off work. We will estimate costs for each category of resource use for each participant, as well as an estimate of total cost for each participant. This will enable an estimate of total and average cost in each study group. We will estimate quality adjusted life years (QALYs) in all three groups for the 12 months of follow-up. This will be done through data collected at 4 time points, baseline; 30 day post-operation, 6-months of follow-up, and 12-months follow-up post-randomisation. As is recommended (Manca et al 2005) QALY gains from the two intervention groups will be estimated using regression based methods to allow for differences between groups in baseline HR-QoL and other relevant patient characteristics. Similar methods will be employed to estimate differences in total costs by groups. As recommended (Gold et al 1996), groups will be ranked in terms of increasing estimated QALYs and both incremental costs and QALYs will be calculated. The outcome measures of the economic evaluation will be estimated in incremental cost-effectiveness ratios. Uncertainty in the estimates of costs and QALYs will be incorporated in by the use of cost-effectiveness acceptability curves (CEACs). CEACS will be estimated by means of non-parametric bootstrapping.

We anticipate, a priori, that our base case analysis will use QALYs estimated by means of the EQ-5D-5L. However, we will also estimate QALYs by means of the SF-6D (derived from the SF-36 data). As part of the analysis, an assessment of the performance of both measures will be made against other data collected as part of PREPARE-ABC. Both instruments will be compared to other clinical and health related measures to compare their relative performance in this group of participants. There is a substantial literature that evaluates the performance of the EQ5D against disease based measures. Generally this is based on correlation and this method will be used for the current study group for both EQ5D and SF6D. For example, against physiological measures of fitness. If there is no compelling evidence that the SF-6D is performing better we will use QALYs estimated from this instrument in a sensitivity analysis.

Missing data can potentially bias results. One potential source of missing data could be non-completion of study eCRF. However, more likely is non completion of patient reported measures such as the EQ5D-5L and SF36, as well as resource use estimates obtained from the patient completed questionnaire. The amount of missing data in the health economic analysis will be scrutinised. Missing data and patterns of missing data will be analysed and discussed between study health economists, study Cls, and statistician. If deemed necessary we will use appropriate statistical techniques, such as

multiple imputation (Rubin et al 2004) to allow for missing data. Imputed data would be used in a sensitivity analysis.

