5.7 Sample Size

An overall sample of 1146 patients (randomised 1:1:1) provides 90% power.

Post-operative complications are evident in 55% of patients by day 30 in patients receiving standard care. To detect a 25% reduction (relative risk 0.75) between standard care and each of the exercise groups (90% power, alpha 2.5%) 343 patients are required in each arm, giving 1029, 10% attrition rate - Total 1146. Average SF 36 score at 1 year is 52 SD 10.To detect a 3 unit difference between standard

care and each of the exercise groups (90% Power, alpha 2.5%) requires 276 in each arm, 3 arms 828, 20% attrition rate. Total 1035.

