5.10.4.5 Analysis Population and Missing Data

The analyses population are defined as:

- a) intention-to-treat: all randomised individuals regardless of adherence;
- b) per-protocol: all randomised individuals who adhere to the study regime attending at least 50% of the hospital supervised exercise sessions or participate in at least 50% of scheduled phone calls with a member of the trial intervention team relative to the treatment arm they are allocated to.
- c) safety population:
 - Arm A all randomised individuals who receive a manual and attended a minimum of one supervised exercise session
 - Arm B all randomised individuals who receive a manual
 - Arm C all randomised individuals

Missing data that occur in outcomes will be multiply imputed to increase precision of the treatment effect estimates. Sensitivity analyses will be conducted to assess the impact of the multiple imputations and a complete case analysis will also be conducted. All imputations will be examined to ensure sensible values are being generated. Imputation models will contain baseline measures, outcome measures and factors predictive of missing data.

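### The economic base case rests in effect on participants with complete data, because imputation is optional and confined to a sensitivity analysis, the reverse of the order set for the clinical outcomes

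*Protocol*

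**What the plan says.** Section 5.10.5.2 of the protocol opens with the declared basis: "The health economic analysis will be carried out on an 'intention to treat' basis". It asks for a total cost for every participant and for QALYs built from EQ-5D-5L at baseline, 30 days after surgery, 6 months and 12 months. Differences in both are to be estimated by regression with adjustment for baseline characteristics, and uncertainty by non-parametric bootstrap.

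The same section accepts that missing data may bias results and says where to expect them: "However, more likely is non completion of patient reported measures such as the EQ5D-5L and SF36", together with the resource-use questionnaire. Its remedy is conditional, "If deemed necessary we will use appropriate statistical techniques, such as" multiple imputation, and the last sentence assigns the role: "Imputed data would be used in a sensitivity analysis".

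Section 5.10.4.5, on the clinical outcomes, says: "Missing data that occur in outcomes will be multiply imputed to increase precision of the treatment effect estimates". It adds that "a complete case analysis will also be conducted". The intention-to-treat population is defined there as "intention-to-treat: all randomised individuals regardless of adherence".

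Section 5.10.5.1 promises a health economic analysis plan (HEAP) before any analysis.

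**The concern.** A QALY over 12 months needs utilities at four time points. A total cost needs, among other items, the resource-use questionnaires at baseline, 6 and 12 months. If the base case uses unimputed data and no other technique is specified, a participant with a missing component has no QALY or no total cost and cannot contribute to that regression.

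Cost-effectiveness appears in both primary objectives (section 4.2.1), so this is not a side analysis. Three things are at stake.

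- **Precision.** Fewer participants inform the incremental estimates.
- **Use of data already in hand.** Section 5.10.5 collects ICU time, length of stay, complications, re-operations and re-admissions from hospital notes or data over 12 months, and regards secondary care as a likely major part of total cost. A total cost that also needs a questionnaire leaves these records unused when the questionnaire is missing.
- **Bias.** If return of forms depends on something that happens after randomisation and is not in the regression, such as a complication, the incremental cost and QALY estimates can be distorted.

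**Working it through.** **Step 1: set the two rules side by side.**

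| | Clinical outcomes (5.10.4.5) | Economic evaluation (5.10.5.2) |
|---|---|---|
| Is imputation done? | Yes, stated without condition | Only if judged necessary |
| Role of imputed data | The stated treatment of missing outcomes | Sensitivity analysis |
| Role of complete cases | Additional analysis | Not named, but what is left for the base case |
| Other method named | None | None |

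The two rules meet on one form. The 12-month SF-36 is a primary outcome and is imputed under 5.10.4.5. The SF-36 also supplies the SF-6D for the alternative QALY (section 5.10.5), where imputation is optional and outside the base case.

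**Step 2: reproduce the protocol's attrition arithmetic.** Section 5.7 gives "3 arms 828, 20% attrition rate. Total 1035" for the SF-36. With a difference of 3, SD 10, two-sided alpha 2.5% and 90% power:

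- n per arm = 2 × (2.241 + 1.282)² × (10/3)² ≈ 276
- 3 × 276 = 828
- 828 / 0.80 = 1035

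The stated figure reproduces, so the 20% is the proportion expected to lack the 12-month SF-36.

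**Step 3: apply that rate to the full sample, as an illustration.** The total of 1146 is from section 5.7. The 20% was planned for the SF-36 and is borrowed here for the 12-month economic forms.

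- 1146 × 0.80 = 916.8, about 917 retained and about 229 not. This is the ceiling, reached only if every loss at an earlier visit falls among those also lost at 12 months.

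**Step 4: add losses at 30 days and 6 months.** The protocol gives no rates for EQ-5D-5L completion at these visits, so the rate m is an assumption. It is taken as the same at both visits and independent across visits. Baseline is taken as complete.

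Proportion with a full EQ-5D-5L series = 0.80 × (1 − m)²

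| Assumed m | Proportion | Of 1146 |
|---|---|---|
| 5% | 0.80 × 0.95² = 0.722 | 827 |
| 10% | 0.80 × 0.90² = 0.648 | 743 |
| 20% | 0.80 × 0.80² = 0.512 | 587 |

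Independence is the pessimistic end and full nesting (80%) the optimistic end. Missing resource-use forms would lower the number with both a QALY and a total cost. No per-arm count is given, because Arm A was suspended under section 5.12 and the arms may be unequal.

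**The case against.** Several objections are serious, and some of them stand.

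*A reader might infer that the results are biased unless data are missing completely at random.* The documents do not support that. Section 5.10.5.2 plans regression with adjustment for baseline quality of life and other characteristics. A correctly specified complete-case regression stays unbiased when missingness depends only on covariates in the model. Bias needs missingness that still depends on the outcome after that adjustment. Complications could act in this way because they are not a baseline covariate, but nothing in the protocol shows that they do.

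*A reader might infer that the protocol prescribes a complete-case base case.* It never uses those words in section 5.10.5. It also does not say that the cost and QALY regressions share one sample. The complete-case reading is a consequence of the rule when no alternative is named.

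*Intention to treat may mean only analysis by allocated arm.* The definition in 5.10.4.5 is chiefly a contrast with the per-protocol set, and the same section itself plans a complete case analysis. So this is better called a poor fit with the declared basis than a plain breach. The poor fit remains: the definition covers all randomised individuals, and section 5.6.2 says that data already collected from people who stop follow-up early will be included on that principle.

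*The HEAP will settle the method, and imputation is only an example of a technique.* Both are true, but the protocol has already given imputed data their place. A HEAP that follows this inherits the weakness, and one that departs from it contradicts the protocol. A technique that is left open is not a named base-case method.

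*The economic and clinical analyses need not share a rule.* Correct, and 5.10.4.5 justifies imputation by precision. The case for change rests on the merits above, with consistency as a supporting reason.

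**Conclusion.** The point holds as a cheap improvement. The protocol fixes a subordinate and optional role for imputation in the economic evaluation, names nothing else for the base case, and so in effect rests that base case on participants with a calculable QALY and total cost. The loss of precision and the setting aside of observed hospital costs follow directly. The bias is conditional on missingness depending on post-randomisation factors outside the regression, which is plausible and unproven.

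The size is illustrative. Only the 20% comes from the protocol, and it was set for the SF-36. It gives at most about 917 of 1146. The 65% figure rests on an assumed 10% at each of two visits and on independence. A reader might take a loss of 20% to 35% as what the plan will produce, but the documents give no completion rates that would support such a forecast.

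**What to change.** In section 5.10.5.2 and in the HEAP, before any analysis is undertaken:

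- make multiple imputation of costs and utilities the base case, carried out by arm, with baseline utility, site, complications and hospital-recorded resource use in the imputation model;
- make the complete-case analysis the sensitivity analysis, which matches the order in 5.10.4.5;
- remove the sentence that confines imputed data to a sensitivity analysis, and the condition that imputation is done only if judged necessary.

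The cost is a wording change in the protocol and HEAP, plus extra programming to combine imputation with the bootstrap used for the acceptability curves. No new data are needed.

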5.11 Data Monitoring

5.11.1 Data Monitoring Committee

Further details of the roles and responsibilities of the Data Monitoring Committee (DMC), including membership, relationships with other committees, decision making processes, and the timing and frequency of interim analyses (and description of stopping rules and/or guidelines where applicable) are described in detail in the PREPARE-ABC DMC Terms of Reference (ToR).

5.11.2 Interim Analyses

No efficacy interim analyses are planned. However, analysis of recruitment rates, withdrawal rates, etc. will be conducted as part of the internal pilot for subsequent publication as documented in the accompanying interim analysis plan.

5.11.3 Data Monitoring for Harm

The DMC will be provided with safety data for each treatment arm including frequency of exercise related adverse events. The committee will advise on the continuation or early stoppage of the trial in the unlikely event that there are concerns over harm to participants.

5.11.3.1 Safety reporting

The principles of ICH GCP require that investigators and sponsors follow specific procedures when notifying and reporting adverse events or adverse reactions in clinical trials. These procedures are described below.

Table 2: Adverse Event Definitions

Adverse Event (AE)	Any untoward medical occurrence in a patient or clinical trial participant and which does not necessarily have a causal relationship with the trial exercise intervention.	
Adverse Reaction (AR)	Any unintended or untoward response to an investigational intervention	
Serious Adverse Event (SAE) or Serious Adverse Reaction (SAR)	 Any AE that at any dose: results in death is life threatening* requires hospitalisation or prolongs existing hospitalisation** results in persistent or significant disability or incapacity is a congenital anomaly or birth defect or is another important medical condition*** 	

^{*} the term life threatening here refers to an event in which the patient is at risk of death at the time of the event; it does not refer to an event that might hypothetically cause death if it was more severe (e.g. a silent myocardial infarction)

^{**} Hospitalisation is defined as an in-patient admission, regardless of length of stay, even if the hospitalisation is a precautionary measure for continued observation. Hospitalisation for pre-

existing conditions (including the planned surgery/elective procedures that have not worsened as a result of exercise) do not constitute an SAE

*** Medical judgement should be exercised in deciding whether an AE is serious in other situations. Important AEs that may not be immediately life threatening or result in death or hospitalisation, but may seriously jeopardise the participant by requiring intervention to prevent one of the other outcomes listed in the table (e.g. a secondary malignancy, an allergic bronchospasm requiring intensive emergency treatment, seizures or blood dyscrasias that do not require hospitalisation, or development of drug dependency).

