5.11.3.2 Clarifications and Exceptions

The intervention under investigation in Prepare ABC is pre- and post-operative exercise. Surgery is conducted in all patients on the trial as part of routine care. All post-operative morbidity up to 30 days post-operation and readmissions up to 90 days are collected as primary and secondary outcome measures in all patients and are not therefore subject to routine safety reporting.

Adverse events include

- An exacerbation of a pre-existing illness
- An increase in frequency or intensity of a pre-existing episodic event or condition
- A condition (regardless of whether PRESENT prior to the start of the trial) that is DETECTED after trial exercise intervention. (This does not include pre-existing conditions recorded as such at baseline as they are not detected after exercise intervention.)
- Continuous persistent disease or a symptom present at baseline that worsens

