5.11.3.3 Exempted Adverse Events

Adverse events do NOT include

- Post-operative morbidity (within 30 days of surgery) this should be graded according to the Clavien Dindo classification and reported on the appropriate eCRF
- Readmissions relating to post-operative morbidities within 90 days of surgery
- Recurrence of primary cancer- this should be reported on the appropriate eCRF
- Death due to primary cancer- this should be reported on the appropriate eCRF
- Medical or surgical procedures; the condition that led to the procedure is the adverse event
- Pre-existing disease or a condition present that was diagnosed before trial entry and does not worsen
- Hospitalisation where no untoward or unintended response has occurred e.g. elective surgery, social admissions

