5.11.3.6.2 Causality and Expectedness

The investigator must assess the causality of all serious adverse events in relation to the exercise intervention using the definitions in Table 2. There are 5 categories: unrelated, unlikely, possible, probably and definitely related. If the causality assessment is assessed as unrelated or unlikely to be related the event is classified as an SAE. If the causality is assessed as possible, probable or definitely related then the event is classified as an SAR.

Expectedness is assessed by trained NCTU staff against a list of events produced by the co-Cls.

If the event is classified as 'serious' and assessed as being related to the exercise intervention then an SAE form must be completed and NCTU notified within 24 hours. If the event is classified as 'serious' and assessed as **not** being related to the exercise intervention or is thought to be related to a post-operative morbidity (POM) these should still be reported to NCTU via the relevant eCRF forms.

If an SAE is considered to be related to the exercise intervention then continuation of the exercise intervention should be discussed with the Chief Investigator

Table 3: Causality definitions

Relationship	Description	Event type	
Unrelated	There is no evidence of any Unrelated SAE causal relationship		
Unlikely to be related	There is little evidence to suggest that there is a causal relationship (e.g. the event did not occur within a reasonable time after administration of the trial medication). There is another reasonable explanation for the event (e.g. the participant's clinical condition or other concomitant treatment)	Unrelated SAE	
Possibly related	There is some evidence to suggest a causal relationship (e.g. because the event occurs within a reasonable time after administration of the trial medication). However, the influence of other factors may have contributed to the event (e.g. the participant's clinical	SAR	

	condition or other concomitant	
	treatment)	
Probably related	There is evidence to suggest a	SAR
	causal relationship and the	
	influence of other factors is	
	unlikely	
Definitely related	There is clear evidence to	SAR
	suggest a causal relationship	
	and other possible contributing	
	factors can be ruled out	

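### The SAE footnote makes exercise causation part of the hospitalisation criterion, so admissions for worsened pre-existing disease not blamed on exercise drop out of SAE counts

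*Protocol*

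**What the plan says.** Table 2 in Protocol section 5.11.3.1 defines an adverse event as one "which does not necessarily have a causal relationship with the trial exercise intervention". An SAE is any such event that meets one of several criteria, among them that it "requires hospitalisation or prolongs existing hospitalisation". The footnote to that criterion places hospitalisation for pre-existing illness outside the definition: "existing conditions (including the planned surgery/elective procedures that have not worsened as a result of exercise) do not constitute an SAE" (the prefix pre- stands before a page break).

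The neighbouring sections treat worsening without reference to cause:

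- Section 5.11.3.2 lists as adverse events "An exacerbation of a pre-existing illness" and "Continuous persistent disease or a symptom present at baseline that worsens".
- Section 5.11.3.3 exempts "Pre-existing disease or a condition present that was diagnosed before trial entry and does not worsen" and also "Hospitalisation where no untoward or unintended response has occurred e.g. elective surgery, social admissions".
- Section 5.11.3.6.1 has the investigator decide whether an event is serious. Section 5.11.3.6.2 then requires the next step: "The investigator must assess the causality of all serious adverse events in relation to the exercise intervention". Events rated unrelated or unlikely remain SAEs and still go to the trials unit through the eCRF.

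**The concern.** Seriousness describes what happened to the patient; causality is a judgement about why. The protocol keeps the two apart everywhere except in this footnote, where an admission for a pre-existing condition becomes serious only if somebody has already put the worsening down to exercise.

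This matters because worsening of existing disease is a plausible route by which exercise could do harm here. ASA I to III patients are eligible (5.3.1.1), and so are patients with previous cardiovascular conditions now judged stable (5.3.1.2). A randomised comparison of serious events is most useful when events are counted in every arm by the same rule, before anyone attributes a cause. The footnote prevents that for one class of admission.

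**Working it through.** No arithmetic applies: the protocol states no admission rate. The check sets the rules side by side and runs cases through them.

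**Two readings of the footnote.** The qualifier stands inside the bracket, next to the planned and elective procedures.

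- Reading 1 (the natural one): it governs all pre-existing conditions, so an admission counts only if the worsening was caused by exercise.
- Reading 2 (the literal one): it governs only planned surgery and elective procedures, so every other admission for a pre-existing condition is excluded, worsened or not.

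| Admission | Footnote, reading 1 | Footnote, reading 2 | 5.11.3.2, 5.11.3.3 and 5.11.3.6.2 with the Table 2 criterion |
|---|---|---|---|
| Planned cancer resection | Not an SAE | Not an SAE | Not an SAE |
| Unplanned, pre-existing illness worsened, attributed to exercise | SAE | Not an SAE | Serious, rated related |
| Unplanned, pre-existing illness worsened, not attributed to exercise | Not an SAE | Not an SAE | Serious, rated unrelated |
| Worsened illness that is fatal, life threatening, disabling or medically important | SAE by another criterion | SAE by another criterion | SAE |

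The third row is the test case. Section 5.11.3.2 makes it an adverse event, the hospitalisation criterion makes it serious, and section 5.11.3.6.2 has a category for it as an unrelated SAE. The footnote says it is not an SAE. Reading 2 resolves nothing, because it also removes the second row.

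**What is lost and what is kept.** Section 5.11.3.6 requires all adverse events to be recorded in the notes and the eCRF, and section 5.10.4.7 tabulates adverse events as well as SAEs. The admission therefore stays in the data as a non-serious event. It loses its place in the SAE table and its five-category causality rating, since section 5.11.3.6.2 requires that rating for serious events only.

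**Dependence on arm.** Under reading 1 an admission counts only if exercise caused the worsening. Arms A and B receive trial exercise; Arm C does not. All arms have CPETs and anyone may exercise unprompted, so attribution in Arm C is not strictly impossible, but it will be rare. The same admission can therefore be an SAE in Arm A or B and not in Arm C. The safety population is defined arm by arm (5.10.4.5) and the DMC receives safety data for each arm (5.11.3), so the comparison mixes two rules. The bias can go either way: counting attributed events only in the exercise arms can create an apparent excess, and leaving out the unattributed ones can hide a real one. Under reading 2 the rule is the same in all arms for unplanned admissions, but they are all lost.

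**Where the gap falls.** Post-operative morbidity to 30 days is outside routine safety reporting in any case. For readmissions to 90 days, section 5.11.3.2 is worded for all of them and section 5.11.3.3 only for those relating to post-operative morbidity. On the wider wording the footnote bites before surgery and after day 90, up to 12 months post-randomisation; these are largely the exercise periods.

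**The case against.** **An exception is not a contradiction.** Sections 5.11.3.2 and 5.11.3.3 define what is an adverse event, while the footnote narrows what is an SAE, so a worsened condition can be the first without being the second. This stands in part: against those two sections the footnote is a poor fit rather than a flat contradiction. The conflict with the separate seriousness and causality steps, and with the unrelated SAE category, remains.

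**The events are not invisible.** All-cause readmission to 90 days is a secondary outcome (5.5.2), and re-admissions over the 12 months of follow-up are taken from notes or hospital data for the economic evaluation (5.10.5). Neither needs attribution to exercise. This stands, and it limits the harm. These sources do not carry an SAE classification or a causality rating, so they do not replace the SAE table.

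**Only exercise-related SAEs need rapid notification.** Section 5.11.3.7.1 sets the 24-hour rule for those alone. That is so, but section 5.11.3.6.2 separately requires serious events judged unrelated to be reported through the eCRF, and the footnote cuts into that requirement.

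**Stronger readings that the protocol does not support.** A reader might infer that the DMC sees only admissions already blamed on exercise. Section 5.11.3 says that its safety data include exercise-related events; it does not limit them to those. A reader might also infer that worsened disease escapes safety recording altogether, but only the hospitalisation criterion is affected and the event is still recorded. Finally, one might assume that an assessor who knows the allocation makes the judgement. Section 5.9.2 describes the teams handling later admissions as blinded and is not explicit about the investigator who classifies the event. The dependence on arm follows from the footnote's wording and does not need that assumption.

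**Conclusion.** The point holds as a defect of definition with a limited reach. For the hospitalisation criterion alone, footnote ** puts a causality judgement inside the seriousness definition, against the protocol's own sequence and its unrelated SAE category. Admissions for worsened pre-existing disease not attributed to exercise drop out of the SAE counts and the causality rating, while staying in the adverse event data and partly visible as re-admissions.

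That some such admissions are wrongly excluded holds on either reading of the bracket. That the SAE tables are not like for like between arms rests on reading 1, which is the natural one. No count of affected events can be given, because the protocol states no admission rate. The change is worth making because sites apply this definition directly and correcting it costs little.

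**What to change.** In footnote ** to Table 2, replace the words that tie worsening to exercise with: that have not worsened since randomisation. Move the qualifier out of the bracket, and state that the exception covers only planned surgery, elective procedures and other admissions for pre-existing conditions that have not worsened.

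An admission for a worsened pre-existing condition then counts as an SAE, with causality rated afterwards under section 5.11.3.6.2. Say explicitly that this is subject to the existing exemptions in sections 5.11.3.2 and 5.11.3.3: post-operative morbidity to 30 days, related readmissions to 90 days, and cancer recurrence. Without that sentence the new wording would pull in events that the protocol deliberately handles elsewhere. Keep the 24-hour form for exercise-related SAEs only.

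The cost is one amended footnote and some extra serious events entered on existing eCRF pages. No visits or assessments are added.
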